Inclusion criteria: 
 1. Enrollment in the Longitudinal Study of the Porphyrins (7201) 2. Willing to sign informed consent form (and provide assent if participant is a minor) 3. Biochemical findings- a marked increase in erythrocyte protoporphyrin [total erythrocyte protoporphyrin >200 ug/dL, or more than 1.5-fold increase (relative to ULN of 80 ug/dL)], with a predominance of free protoporphyrin (85-100% in EPP and 50-85% in XLP). 4. Molecular findings – one of the following: 
 a. A disease causing FECH mutation trans to the IVS3-48C>T low expression FECH allele b. Two disease-causing FECH mutations c. A gain-of-function ALAS-2 C-terminal deletion/exon 11 mutation (in XLP). 
If no mutation is found and subjects fulfill criteria 1-3 they are eligible for enrollment

Exclusion Criteria: 
 1. Elevations of porphyrins in urine, plasma or erythrocytes due to other diseases (i.e. secondary porphyrinuria or porphyrinemia), such as liver and bone marrow diseases [13].

2. A diagnosis of porphyria that cannot be documented by review of existing medical records or repeat biochemical or DNA testing.

Primary Objectives:

1. Systematic characterization of the phenotypic, psychosocial, biochemical, and molecular data for EPP and XLP;
2. Longitudinal investigation and analysis of pertinent issues involved in prognosis for the erythropoietic protoporphyrias, including morbidity, development of disease complications, and outcomes of commonly used treatments, as well as more advanced treatments such as liver or bone marrow transplantation, and new photoprotective drugs now under investigation;
3. Identification of biochemical features (biomarkers) that may predict future symptomatic episodes so that interventions can be initiated before symptoms develop; and
4. Provide a resource of well-documented data, samples, and subjects that may be available for other studies, including genetic studies (predictors, biomarkers, modifying genes, etc.), mechanistic investigations, and clinical trials.

Statistical Considerations (sample size and analysis plan):

1. Sample size: 150
2. Analysis plan:
 - a. Correlations between QoL scale scores, clinical severity measures and genotype will be computed. The clinical course and severity of patient will be described.

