 - b. Relationships between clinical and laboratory values will be evaluated in longitudinal mixed effect models. We will develop models that capture the combined frequency and severity of disease manifestations while accounting for age of onset, protoporphyria subtype (EPP and XLP), and genotype. A sample size of 150 (assuming a minimum of 3 follows ups per patient, a correlation of 0.7 among outcomes over time from the same subject, a variance of outcome equal to 1 and a compound symmetric covariance structure) yields 91% power to detect a moderate interaction ($\beta=0.4$) between time and an associated factor of interest.
 - c. A severity score based on predictive demographic and clinical characteristics will be developed
 - d. After 100 participants are enrolled, the mean score of the Hospital Anxiety and Depression Scale (HADS) will be computed and compared to the general population value. A sample size of 100 yields 90% power to detect a 20% difference in HAD-scale between the general population and our sample at the .05 significance level. The illness Perception Questionnaire and EPP/XLP-specific questionnaire will also be scored.
 - e. During this interim look at $n=100$, we will re-evaluate the estimates used in our initial power calculation that yielded a sample size of 150 and determine whether the study needs to be extended beyond this point to examine correlations of QoL scale scores with clinical severity and genotypes

Sponsors (federal, state, foundation and industry support): National institutes of Health (NIH)

1. Protocol Overview

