6. Statistical Considerations

6.A Analysis Plan

General Statistical Considerations

Natural history study and genotype analyses: This is an observational study aimed to provide a systematic description of the severity and clinical course of each patient with the EPP phenotype, develop a severity score and correlate genotype with phenotype for EPP and XLP. Continuous variables representing patient demographic and clinical characteristics will be summarized using means and standard deviations or medians and quartiles as appropriate, while categorical variables will be summarized by frequencies with 95% confidence intervals.

A major objective will be to identify the FECH and ALAS2 mutations in each patient with the EPP-phenotype. In patients with the phenotype and no detectable FECH or ALAS2 mutations identified, a second independent blood sample will be obtained to confirm the absence of FECH and ALAS2 mutations, followed by whole exome sequencing. Exome analysis will be performed at the Mount Sinai Institute for Genomics and Multiscale Biology as described above in more detail.

Clinical and Laboratory Analyses: Clinical and laboratory measurements will be collected/described at each visit. We will develop models that capture the combined frequency and severity of disease manifestations while accounting for age of onset, protoporphyria subtype (EPP and XLP), protoporphyrin levels and genotype. To account for multiple observations obtained for each patient during the follow-up, we will develop linear mixed effects models that account for the main effect of interest and its change over time, correlated data associated with repeat measurements on the same persons, random effects of clinical center and patient, as well as the effects of confounding variables and any modifiers of the main effect. To assess the statistical significance of the effects of biochemical levels alone and these levels by age of patient, we will use a t-test to evaluate whether the coefficient of the interaction between biochemical level alone and biochemical levels by age differs from zero.

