- 1) Characterizing EPP and XLP Illness Perception via the Illness Perception Questionnaire, dermatology-specific QOL via the Dermatology Life Quality Index and EPP-specific QOL via the EPP/XLP specific questionnaire. The mean and standard deviation of each scale in our sample will be assessed.
- 2) Scores for all four QOL assessments will be analyzed; FECH and ALAS 2 mutations correlations will be sought with clinical parameters, disease severity score and genotypes.

Secondary analyses will inform whether a study extending beyond 100 patients will be needed to examine correlations of QOL scale scores with clinical severity and genotypes.

6. B Power Calculation

For the proposed analyses, the statistical powers are of two sided tests, with 0.05 level of significance.

Linear mixed effects model: We may assume, for example, that 150 participants will have at least 3 follow up visits per subject. Taking into account the correlation among outcomes over time from the same subject, the main interest is in determining whether the regression coefficient of the interaction between time and covariate of interest is zero or not. Using GPower 3.0, Table 6-1 shows the results when the variance of outcome is equal to 1, where ρ and β denote correlation among repeated outcome measures and effect size of the interaction, respectively. In this calculation, we assume compound symmetry for the covariance structure of repeated outcome measures from the same subject and the same number of subjects in each group with/without a potential factor of interest. The study is certain to detect moderate ($B \geq 0.4$) differences in the analysis.

Table 6-1. Power calculation for linear mixed effects model based on the most common types of porphyria (AIP and PCT)

Sample size	ρ	B for time x factor of interest	Power
150	0.5	0.3	0.45
		0.4	0.72
		0.6	>0.99
	0.7	0.3	0.67
		0.4	0.91
		0.6	>0.99

7. Data Management

All study data will be collected via systems created in collaboration with the RDCRN Data Management and Coordinating Center and will comply with all applicable guidelines regarding patient confidentiality and data integrity.

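### Section 6.A does not separate between-patient from within-patient effects of biochemical level, so an undivided level effect could not by itself support claims about monitoring or early warning

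*Combined protocol and SAP*

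**What the plan says.** The Synopsis (Statistical Considerations, item 2b) states: "Relationships between clinical and laboratory values will be evaluated in longitudinal mixed effect models". Section 6.A, under Clinical and Laboratory Analyses, gives these models random effects for clinical center and patient, plus confounders and effect modifiers. The models are then used "To assess the statistical significance of the effects of biochemical levels alone and these levels by age of patient", and the test named is a t-test on an interaction coefficient. How level is coded is not stated: there is no patient mean, no deviation from it and no change score.

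Primary objective 3 in the Synopsis seeks biochemical features that may "predict future symptomatic episodes so that interventions can be initiated before symptoms develop". The opening of Section 4.I adds the aim of judging biomarkers for predicting and monitoring severity. Research question B in Section 2 asks for markers of disease severity.

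Section 4.I, items 1 and 2, bears on the same models in general terms. Enrollees are characterised at baseline, including biochemically. Status at enrollment is to be adjusted for so that analysis can concentrate on change during follow-up, and time-dependent covariates are foreseen. It does not say that baseline biochemical level enters the Section 6.A model.

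**The concern.** Porphyrin level varies between patients and, to an extent not yet known, within a patient over time. A random-intercept model with one coefficient for level returns a weighted average of the two associations. It is unbiased for the within-patient association only if the patient intercept is unrelated to the marker. The protocol gives reasons to doubt that: Section 4.H.1 ties severity partly to genotype, Section 4.G describes survivor bias and biases from severity and access to care, and Section 4.I expects early enrollment to favor longer-term cases.

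The two associations answer different questions. Early warning and monitoring ask whether a rise in this patient's level goes with worse disease in this patient. Prognosis and severity marking can properly use stable differences between patients. A blended coefficient cannot show which one it reflects. It can suggest a warning signal where none exists, and it can dilute or cancel a real one.

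Age has the same structure. Age at a visit combines age at entry, which carries cohort and survivor differences, with ageing during follow-up.

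**Working it through.** **Inputs from the documents.** Section 6.B: "the statistical powers are of two sided tests, with 0.05 level of significance"; "150 participants will have at least 3 follow up visits per subject". Synopsis item 2b: "a correlation of 0.7 among outcomes over time from the same subject" (Table 6-1 also shows 0.5), with "a variance of outcome equal to 1 and a compound symmetric covariance structure".

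**Assumptions not in the documents.** Four visits (baseline plus three follow-ups), marker SD 1, marker intraclass correlation (ICC) 0.5, 0.8 or 0.9, between-patient effect 0.2 or 0.4, balanced visits, no center effect, no missing data. No ICC is given because Section 4.H.2 lists the stability of porphyrin levels as a study question.

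**Step 1: the plan's own figure.** The plan says that its design "yields 91% power to detect a moderate interaction" of 0.4. I used a repeated-measures within-between F test with two groups, m measurements, non-centrality λ = f²·N·m/(1−ρ) and df = (m−1) and (N−2)(m−1). The mapping f = β√(m−1)/(2m) is inferred; the documents do not give it.
- m = 3: f² = 0.16 × 2/36 = 0.00889; λ = 0.00889 × 150 × 3/0.3 = 13.33; power 0.912.
- m = 4: f² = 0.16 × 3/64 = 0.0075; λ = 0.0075 × 150 × 4/0.3 = 15.0; power 0.914.

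The stated 0.91 is reproduced, and the other cells agree within 2 points. This calculation covers a two-group factor by time, with equal groups. It neither supports nor refutes the point about a time-varying marker.

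**Step 2: what one coefficient averages.** With m visits, outcome correlation r and marker ICC, the information per patient is
- within: (m−1)(1−ICC)/(1−r)
- between: m[ICC + (1−ICC)/m]/[(1−r) + m·r]

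At m = 4, ICC 0.8, r 0.7: within = 3 × 0.2/0.3 = 2.00; between = 4 × 0.85/3.1 = 1.10. The weight on the within-patient effect is 2.00/3.10 = 0.646. With a true within-patient effect of zero and a between-patient effect of 0.4, the single coefficient is about 0.354 × 0.4 = 0.142. The observed patient mean is a noisy version of the true one (factor 0.8/0.85 = 0.941), which gives 0.133. The simulated average was 0.129.

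The weight depends on the inputs: 0.288 at ICC 0.9, r 0.5 (0.60 within, 1.48 between) and 0.861 at ICC 0.5, r 0.7 (5.00 within, 0.806 between).

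**Step 3: simulation.** Random-intercept model fitted by maximum likelihood, N = 150, four visits, 600 replicates per scenario, true within-patient effect zero. Share of studies in which the undivided level term is significant:

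| Outcome correlation | Between-patient effect | ICC 0.5 | ICC 0.8 | ICC 0.9 |
|---|---|---|---|---|
| 0.7 | 0.2 | 12% | 31% | 49% |
| 0.7 | 0.4 | 21% | 75% | 96% |
| 0.5 | 0.2 | 18% | 49% | 69% |
| 0.5 | 0.4 | 43% | 96% | 99.5% |

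Over the same 12 scenarios:
- separated within-patient term: 4% to 6%
- undivided level with baseline level as a covariate: 6% to 21% (12% at ICC 0.8, correlation 0.7, effect 0.4)
- baseline level and baseline outcome as covariates: 5% to 13%
- level-by-age interaction: 4% to 6.5%

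Adding level-by-age to the model leaves the level term almost unchanged (21%, 74% and 95% in the second row). If the marker has no effect of either kind, the undivided term rejects in 4% (1,000 replicates).

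**Step 4: the other direction** (ICC 0.8, correlation 0.7).
- True within-patient effect 0.2, no between-patient effect: power 93% for the split term, 80% for the single term.
- Between +0.4, within −0.2: the single term averages −0.02 and rejects in 10%; the split within-patient term rejects in 93%.

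**Step 5: precision cost.** At ICC 0.8, r 0.7, the standard error is 1/√(150 × 2.00) = 0.058 for the within-patient term and 1/√(150 × 3.10) = 0.046 for the single term, a ratio of √(3.10/2.00) = 1.24.

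**The case against.** The plan does not commit to a single undivided term. Section 6.A says that models will be developed and leaves the coding open, so one-term coding is an inference from silence. That is correct. The point is that the coding needs to be stated, because the ordinary reading of the text blends the two effects.

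A reader might infer that the t-test named in Section 6.A is itself inflated. It is not. Read literally it concerns an interaction, and the level-by-age test kept about its nominal size. The exposure lies in the effect of level alone, which the section says will be assessed but for which it defines no clear test.

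Section 4.I already plans control for status at enrollment, and Section 6.A accounts for genotype and subtype. If baseline level were among the covariates, most of the excess would go. This stands, with two limits: the text does not commit to baseline level in this model, and 6% to 21% remains.

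A reader might also infer that a marker that never moves with symptoms would be declared fit for monitoring, or that all of objective 3 must rest on the within-patient term. The documents support neither. No rule for declaring a biomarker exists, so the harm lies in interpretation. A stable between-patient marker can also identify who is likely to have episodes, and it suits research question B. Finally, the HADS comparison, which Section 6.A calls the primary outcome, is untouched.

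**Conclusion.** The concern holds as a gap in specification. Nothing in the plan separates between-patient from within-patient effects of biochemical level, and an undivided level effect cannot by itself support statements about monitoring or early warning. With no within-patient effect, such a term was significant in 12% to 99.5% of simulated studies, or 6% to 21% with baseline level added, against 4% to 6% for a separated term. The width of the first range reflects inputs that the documents do not give, chiefly the marker ICC and the size of the between-patient effect, so no single rate should be quoted as the plan's error rate. The problem is largest if porphyrin levels prove stable within patients. The conclusion covers the level main effect, not the level-by-age interaction.

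**What to change.** In Section 6.A:

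1. Enter each time-varying biochemical level as two terms, the patient's mean and the visit's deviation from that mean, and report both coefficients.
2. State that claims about monitoring or early warning (primary objective 3 and the opening of Section 4.I) rest on the within-patient term, and that the between-patient term is reported as a marker of prognosis or severity.
3. Split age into age at enrollment and time since enrollment in the level-by-age model.

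The cost is SAP wording and one extra coefficient per marker; no new data are needed. The interval for the within-patient effect will usually be wider, about 1.24 times in the worked case.

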- 1) Participants and their family members known to the investigators who can be re-contacted and consented for inclusion, or who have previously consented for the procedures that are part of this study.
- 2) Individuals referred by the American Porphyria Foundation with known or suspected porphyria.

- 3) Individuals referred by physicians and other sources.

4.A. Inclusion criteria

There will be no exclusions based on age, race, ethnicity, or gender for this study. Inclusion criteria are based on 1) clinical features, 2) biochemical findings, as documented by laboratory reports of porphyria-specific testing performed after 1980, and 3) molecular findings documenting the identification of a mutation in a porphyria-related gene. Absolute values are preferred for diagnostic biochemical thresholds. Fold increases in comparison to an upper (or lower) limit of normal (ULN or LLN) are also acceptable, but are complicated by considerable variation between laboratories in normal limits. Equivocal biochemical measurements may require confirmation by a consortium reference laboratory. Provision is made for enrolling relatives who may not have symptoms but have biochemical or molecular documentation of a porphyria.

1. Enrollment in the Longitudinal Study of the Porphyrins (7201)
2. Willing to sign informed consent form (and provide assent if participant is a minor)
3. Biochemical findings- A marked increase in erythrocyte protoporphyrin [total erythrocyte protoporphyrin >200 ug/dL, or more than 1.5-fold increase (relative to ULN of 80 ug/dL)], with a predominance of free protoporphyrin (85-100% in EPP and 50-85% in XLP).
4. Molecular findings – one of the following:
 - a. A disease causing FECH mutation trans to the IVS3-48C>T low expression FECH allele
 - b. Two disease-causing *FECH* mutations
 - c. A gain-of-function *ALAS-2* C-terminal deletion/exon 11 mutation (in XLP)

If no mutation is found and subjects fulfill criteria 1-3 they are eligible for enrollment

We expect to enroll 150 patients with EPP/XLP.

4.B. Exclusion Criteria

We will exclude cases with elevations of porphyrins in urine, plasma or erythrocytes due to other diseases (i.e. secondary porphyrinuria or porphyrinemia), such as liver and bone marrow diseases [Gibson 2000]. We will also exclude patients with a prior diagnosis of porphyria that cannot be documented by review of existing medical records or repeat biochemical or DNA testing.

4.C. Recruitment and Enrollment of Subjects

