Table 1. CRFs Collected at Baseline and Follow-up Visits

CRFs	Visits			
	Baseline	Annual Follow-up ¹	Interim Event	Acute Symptom Phase
Completed for Longitudinal Study of the Porphyrrias (7201)				
Eligibility	X			
Sociodemographics	X	X ²		
Demographics	X			
General Medical History	X	X ²	PRN	
Concomitant Medications	X	X ²	PRN	
Family History (complete pedigree to be maintained as a source document)	X	X ²		
Baseline Disorder Specific Information: Erythropoietic Protoporphyrria	X			
Disorder Specific Information- Annual Follow-up: Erythropoietic Protoporphyrria		X		
General Physical Exam	X	X	PRN	
Porphyria Specific Lab Tests	X	X	PRN	
Local Lab Tests	X	X	PRN	
Adult PROMIS-57 Questionnaire (≥18 years old) OR Pediatric PROMIS Short Form Questionnaires- Depressive Symptoms, Anger, Anxiety, Fatigue, Pain Interference, Peer Relationships (7-17 years old)	X	X		
Completed for this Study (7207)				
7207 Eligibility	X			
EPP Specific Labs	X	X	PRN	
Hospital Anxiety and Depression Scale (HADS) (≥ 18 years old)	X	X		
EPP Specific Quality of Life Questionnaire (≥ 18 years old)	X	X		PRN
Illness Perception Questionnaire (IPQR) (≥ 18 years old)	X			
PedsQL Quality of Life Inventory (2-18 years old and parent proxy) **NOTE- a pediatric patient in 7207 does NOT need to complete the Pediatric PROMIS Short Forms	X	X		
PROMIS Pain Interference section (≥ 18 years old)				PRN
PedsQL Pediatric Pain Questionnaire (5-18 years old and parent proxy)	X	X		PRN

¹ Follow-up study visits or contacts by site coordinator will be at least on an annual basis. Symptomatic subjects will be followed as needed

² Update as appropriate

PRN= as needed

Medical record review: Local and outside medical records will be obtained, with appropriate consent, for all participants. At the time of enrollment, the participants will be asked to give permission to obtain all past and future medical records. This will provide more complete information on the clinical course of the disease, including retrospective data. To reduce unnecessary heterogeneity of the data, we will initially limit this procedure to the living participants who were diagnosed with porphyria after 1980.

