Disease Severity Score: Clinical and laboratory values assessed above will be considered potential variables to be included in an overall disease severity score. The distributions of the proposed variables to be included in the severity score will be assessed for utility to the severity score calculation. Considerations for variable utility include sufficient variability in the disease population and interrelationships with other proposed variables (if two variables are highly correlated one will be removed from the score calculation). Variables chosen to be included in the severity score will be assigned categorical ranks based on individual severity and then summed to get an overall disease severity score. The utility of the severity score will be assessed by correlating the score with clinical outcomes.

Psychosocial Impact: The following questionnaires will be administered: a) the Hospital Anxiety and Depression Scale will be used to determine the levels of anxiety and depression in these patients. These data will be scored as per the established protocol and compared to the published age-matched norms; b) the Illness Perception Questionnaire will determine the disease impact and understand how patients think and feel about their disorder. This questionnaire will determine if certain groups, such as younger adults, are more significantly impacted by this disease. The questions are scored on a Likert scale and higher scores indicate greater impairment; c) a recently validated EPP/XLP-specific questionnaire

developed in Europe will more specifically evaluate disease impact on daily functioning. After the target enrollment of n=100 is reached, we will begin the analysis.

Our primary outcome is verifying that EPP and XLP patients have higher than normal anxiety and depression. We will compare the mean Hospital Anxiety and Depression Scale (HADS) of our sample with the general population Scale (mean = 9.82, SD=5.98) (16). The null hypothesis is that there is no difference in HADS score between the general population and EPP/XLP patients.

With a sample size of 100, using a two-tailed 0.05 level one-sample t-test we will be able to detect a 20% difference in scale between the general population and our sample with 90% power.

Secondary analyses include:

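### The plan promises age-matched norms for HADS, but its primary test uses one general-population mean (9.82) of unstated age make-up

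*Combined protocol and SAP*

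**What the plan says.** Section 6.A, Psychosocial Impact, describes the HADS comparison twice.

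- In the list of questionnaires, item (a): "These data will be scored as per the established protocol and compared to the published age-matched norms".
- In the definition of the primary outcome: "Our primary outcome is verifying that EPP and XLP patients have higher than normal anxiety and depression". The comparison is then set out as "We will compare the mean Hospital Anxiety and Depression Scale (HADS) of our sample with the general population Scale (mean = 9.82, SD=5.98", with the hypothesis "The null hypothesis is that there is no difference in HADS score between the general population and EPP/XLP patients". The sample-size sentence takes 100 participants and 90% power, "using a two-tailed 0.05 level one-sample t-test we will be able to detect a 20% difference in scale".

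The Synopsis (Statistical Considerations, item 2d) follows the second description: "the mean score of the Hospital Anxiety and Depression Scale (HADS) will be computed and compared to the general population value". It does not mention age.

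Two other provisions bear on who supplies the scores. Section 4.A states "There will be no exclusions based on age, race, ethnicity, or gender for this study", and Table 1 restricts the instrument to adults: "Hospital Anxiety and Depression Scale (HADS) (≥ 18 years old". The age mix of the HADS sample is therefore whatever adult recruitment produces.

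**The concern.** A one-sample test against a fixed number is not matched on anything. It asks whether the sample mean differs from 9.82. It does not ask whether these patients score higher than people of their own ages. The two questions coincide only if the population behind 9.82 has the same age mix as the enrolled adults, or if HADS does not vary with age. The documents state neither, and by promising age-matched norms in item (a) the plan itself treats age as relevant.

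The study has no internal control group, so the reference value carries the whole inference. If the mean expected from the participants' ages is above 9.82, the test can reject with no disease effect. If it is below 9.82, a real excess can be missed. The two comparators can also give different answers, and the plan does not say which one governs.

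**Working it through.** **Does anything in the documents reconcile the two comparators?**

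- The 9.82 value is cited only as reference (16). The reference list in Section 9, as supplied, is unnumbered and contains no HADS source. The age make-up of the reference population is not given.
- Section 4.I (stratification, baseline covariates, confounders) and the mixed models in Section 6.A concern estimates within the cohort. They do not adjust a comparison with an external constant.
- No section defines age-specific norms, age bands or an age standardisation for HADS.

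**Inputs.** From Section 6.A: mean 9.82, SD 5.98, n = 100, two-sided alpha 0.05, difference 20%. Assumed here, because the documents give no figures: a mismatch *b* between 9.82 and the mean expected from the participants' ages, and a scenario in which 70 of the first 100 participants are adults.

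**Formula.** The one-sample t-test has df = n − 1 and noncentrality λ = (shift / SD) × √n. Power is P(|T| > t crit) under the noncentral t distribution.

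**Step 1: reproduce the plan's figure.** The difference is 0.20 × 9.82 = 1.964 points, and 1.964 / 5.98 = 0.328. With n = 100, λ = 0.328 × 10 = 3.28, and power is 90.2%. The smallest n reaching 90% is 100. The stated power is right, and it is the power of the single-constant test. At n = 100, with t crit = 1.984, an observed difference of 1.984 × 5.98 / 10 = 1.19 points is significant.

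**Step 2: no disease effect, mismatch *b* upward (shift = *b*).** Two-sided rejection rate:

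| *b* (points) | 100 adults | 70 adults |
|---|---|---|
| 0.1 | 5.3% | 5.2% |
| 0.25 | 7.0% | 6.4% |
| 0.5 | 13.1% | 10.6% |
| 0.75 | 23.7% | 17.9% |
| 1.0 | 38.1% | 28.1% |

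For example, with *b* = 1.0 and n = 100, λ = (1.0 / 5.98) × 10 = 1.67.

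**Step 3: true 20% excess, mismatch in the opposite direction (shift = 1.964 − *b*), 100 adults.** Power falls from 90.2% to 87.0%, 81.0%, 67.9%, 52.0% and 35.8% for the same five values of *b*. For example, with *b* = 1.0 the shift is 0.964 and λ = 1.61.

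**Step 4: power of an age-matched test.** The analysed variable becomes observed score minus age-band norm, and its SD need not be 5.98. For a 1.964-point mean difference:

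| Assumed SD of the difference | 100 adults | 70 adults | Adults needed for 90% |
|---|---|---|---|
| 5.5 | 94% | 84% | 85 |
| 5.98 | 90% | 77% | 100 |
| 6.5 | 85% | 70% | 118 |
| 7.0 | 79% | 64% | 136 |

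**The case against.** The strongest reply is that the two statements are compatible. Item (a) sits in a list saying what each questionnaire is for, and a later paragraph defines the primary test. Both comparisons may be intended, in which case the age check is already planned and only a sentence on hierarchy is missing. That reading is possible, but the plan does not say it. Even if it is right, the test behind the primary claim remains the unmatched one.

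Second, the bias depends on a source that cannot be seen. The 9.82 value might come from a population of similar age or already be age-standardised, and the documents do not show that HADS varies with age. The unresolved citation may be only a numbering fault, since the Synopsis exclusion criteria also carry a bracketed number, [13], that the list cannot resolve. This stands as a limit on what can be claimed: a biased result is possible, not demonstrated. Stating the age make-up of the source would help settle it.

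Third, the offsets are chosen, not derived, and 1.0 point is about half the 1.964-point target. That is correct, and the figures are a sensitivity range only. The 70-adult column reflects the adults-only instrument and is a separate assumption. It matters here only because power must be rechecked in any case.

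Fourth, none of the Synopsis's four Primary Objectives is a HADS test, and Section 4.G accepts that bias is inevitable in this design. But Section 6.A calls this the primary outcome and gives it a null hypothesis, an alpha and a power, so its reference value deserves the same care.

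**Conclusion.** The concern holds. Section 6.A promises age-matched norms and then tests the primary outcome, as the Synopsis does, against one general-population mean whose age make-up is not given. No other section closes that gap.

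The conflict is certain from the text, but the size and direction of any resulting bias are not known. On the assumed offsets (SD 5.98, 100 adult scores), a mismatch of 0.1 points is negligible. At 0.5 to 1.0 points, false rejection is 13% to 38% in one direction, and power is 68% to 36% in the other. The plan's 90% power is arithmetically sound but belongs to the unmatched test. The change should be made before the n = 100 analysis, so that the comparator is not chosen after the results are seen. Sex mix is a separate question: the plan promises no sex matching, and Section 8.A only expects equal numbers of males and females.

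**What to change.** Make the age-matched comparison the primary test:

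1. For each adult, compute the observed HADS score minus the published norm for that person's age band (and sex, where the source gives it). Test whether the mean difference is zero with the same two-sided one-sample t-test at 0.05.
2. Name the norm source and its age bands before analysis.
3. Keep the comparison with 9.82 as a sensitivity analysis, and state the source and age make-up of that value.
4. Restate power using the SD of the observed-minus-norm difference and the number of adults expected at the n = 100 look. Align the Synopsis with Section 6.A.

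The cost is wording in the analysis plan and Synopsis, one named source and a revised power statement. No new questionnaire or visit is needed. There are three practical conditions. Suitable age-band norms must be found, although item (a) already presumes that they exist. Section 4.E.2 keeps date of birth at the sites, so confirm that age in years at HADS completion is in the central data file; the models in Section 6.A already use patient age. Finally, the 90% figure may change, as the last table in the working shows.
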